Lung Cancer Surgery: Decisions Against Life Saving Care - The Intervention

NCT01687738

Protocol Date: May 13, 2011

Most Recent IRB Approval Date: March 29, 2016

Lung Cancer Surgery: Decisions Against Life Saving Care - The Intervention

STUDY PROTOCOL

A. Overview: We propose a multiple site, imbedded randomized clinical trial. Overall lung surgery rates and black / white disparities have not improved during a decade of documentation [38]. We will establish baseline rates of surgery at each site accounting for race and co-morbid illness using a 2-year retrospective chart review. All patients with Stage I or II non-small cell lung cancer who enroll in the study will be entered into real time registries at every site and patients' progress through the registries including follow-up provider visits, diagnostic tests, and procedures will be transparent to lung cancer providers. The randomized trial will compare patients who receive usual care to those who receive visits and calls from a trained cancer communicator who is well versed in issues specific to lung cancer and trained in active listening and communication that accounts for patients' limitations in health literacy.

B. Description of the Study Areas: The proposed study area is comprised of 3 North Carolina sites (Chapel Hill, Greensboro, and Greenville), in addition to Columbia, South Carolina (Appendix G). One is purely staffed as an academic medical center (AMC) for which the hospital has no community staff members, two have a mix of academic-based and community practices, and one consists entirely of community practices. In addition to the mix of practice settings, both urban and rural geographic settings with large African-American populations will be included. We have successfully recruited at all 4 sites in our recent prospective study. The selection of these sites was motivated by 4 considerations: (i) the university hospitals have large referral bases that concentrate many lung cancer patients in a few focused areas. ECU and the MCHS are partners in the community engagement core of the UNC CTSA. We will take advantage of CTSA infra-structure to execute a multi-modal intervention that will translate into improved lung cancer care. We will also involve the education core of the CTSA to help train students and fellows interested in cancer-related translational research.

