C. Early Stage, Non-Small Cell, Lung Cancer Cases: The table below includes number of patients from 2007 with stage I and II, non-small cell lung cancer entered in each local cancer registry. These data only include patients with tissue proven diagnoses and not those who had CT lesions with extremely high cancer probability and refused surgery or dropped out of follow-up (we did include these patients in our prospective study). Therefore, eligible patients are underestimated while "percent surgery" rates are overestimated when factoring in all patients with early stage, non-small cell disease.

Site	Number of Cases	African-Americans	Percent Surgery
ECU	63	11	70
MCHS	141	24	69
UNC	57	14	74
USC	66	17	75

From our prospective study, we anticipate an average recruitment rate of 70% across sites. Only 11% of all patients approached during the post-diagnosis – pre-treatment recruiting interval refused participation and there was no difference by race.

D. Retrospective Chart Review: Our recently completed study demonstrated that co-morbid

conditions differentially affected black patients' care. Given these data, during the first six months of the intervention trial we will perform a retrospective chart review for the 2008 and 2009 calendar years. We will review all patients diagnosed with stage I or II, non-small cell cancer to serve as a baseline for surgical rates and to examine outcomes of patients treated with and without surgery using a very specific analysis of co-morbid conditions and severity. These data will be checked against Strand's report [45] to assess compatibility and level of detail. The results will be used by our expert panel of co-investigators and site investigators to create an educational checklist to remind lung cancer providers that surgical contra-indications are often relative and subjective. We anticipate the availability of approximately 100-150 charts per site in the 2-year pre-study window. Charts will be selected using appropriate ICD-9 billing codes. Data will be collected in an aggregate manner and no linkage files or specific patient identifiers will be maintained.

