E. Prospective Study: All sites will begin recruiting patients by the beginning of study Month 13. As most cancer programs have at least rudimentary patient tracking and navigation, this degree of usual care will serve as the control. All providers will receive the co-morbid illness educational checklist at all sites and will receive monthly data concerning surgical rates by comorbid condition and race. Patients will be randomized to either usual care or a more intense communication intervention delivered by a trained cancer communication educator as described below. Since we are building on the methods of our prior cohort study, pretesting of recruitment methods and study instruments can proceed quickly before randomization. Lung cancer surgery rates in the control groups will be compared to historical controls at the individual sites to account for a passive effect of the registry and educational checklist. As care registries and data compilation by race is a mandate of the HITECH portion of the American Recovery and Reinvestment Act, we don't believe that it's ethical to deny any group access to the registry. Given the flat rate of lung cancer surgery and persisting racial gap documented for over a decade in datasets of national scope [7, 36, 38], historical controls for this portion of the study are justified.

1. Inclusion and Exclusion Criteria for Patients

We will enroll patients who meet these criteria: (1) age 21 years or greater; (2) a probability of 60% or higher of a lung lesion being malignant as calculated by Bayesian analysis derived from clinical and radiographic criteria or, alternatively, biopsy proven disease; and (3) the patient has received a clinical classification of stage I or II disease. By "clinically classified", we mean using all studies including CT scans, PET scans, bone scans, mediastinoscopy, and / or any study or procedure performed short of thoracotomy.

We will exclude patients from this study for 3 reasons: (1) incarceration / ward of the state status, (2) severe cognitive impairment, (3) absolute contraindications by pulmonary function testing, or (4) Non-English speaking. Hispanic patients represent less than 4 percent of lung cancer patients in North Carolina restricting our ability to document an intervention effect.

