Given the ratio of catchment area patients that receive their lung cancer care at each study site and a conservative, estimated an overall recruitment rate of 50%, we will be able to recruit 165 stage I and II patients per year combining all study sites. We anticipate 3 yrs of patient recruitment with the accrual of 496 patients. We will oversample black patients, as we did in our prospective study, to attain an enrollment goal of 30%.

3. The Interview and Survey Instruments

Patient Interview. We will administer the surveys as face-to-face interviews, conducted by

thoroughly trained RAs at each site. We will attempt to arrange interviews at the convenience of the patient. Before the project begins we will give all RAs a script and provide rigorous training in its use so that interview technique and content will be consistent at all sites; we will also develop and provide training manuals. We will interview patient-participants in private settings. For onsite interviews, we will identify rooms in the same building or adjacent buildings that are apart from clinic. Offsite interview venues will include the investigator's institution, the patients' homes, or other mutually agreeable locations. All interview sites will be private and secure. If patients require more than one sitting to complete the survey because of fatigue or time constraints, we will accommodate such needs.

Patient Questionnaire. The proposed instrument builds on our preliminary work (Appendix E) by formally measuring health literacy. Low literacy likely identifies patients for whom the communication intervention might be more needed and effective. The questionnaire also covers the following constructs and relies on reliable and validated items or batteries drawn from previous instruments. Specifically areas included will be:

1. *Demographic Information:* age, sex (recorded only by interviewers, not asked), marital status, race, educational attainment, estimated household income, type of health insurance, access to a regular source of care, and affiliation with any church or denomination.
2. *Health Status:* Physicians may use poor physical or emotional function as a contraindication for cancer surgery; patients may opt against surgery because of poor health-related quality of life. We will use the SF-12 [23], to assess this domain. (Appendix C)
3. *Health Literacy:* Test of Functional Health Literacy in Adults-short form [61] (Appendix C)

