We will analyze patient level cross-sectional dichotomous outcome data using logistic regression growth models. We will both limit analyses to the cancer communicator control group and do an all enrollee analysis by adding a communicator intervention / no communicator intervention predictor variable to the models. First, we will fit a saturated growth model to estimate annual proportions of these outcomes, before and after the registry/feedback intervention, to assess the effects of the intervention on these outcomes by contrasting the proportions before and after the interventions. We will test the null hypothesis that the proportions before and after the intervention are the same. We will repeat this analysis by including "race" and "race x time" interaction in this model to examine changes in these outcomes between the two races and also if there are any differential changes over time. We will test the null hypothesis that the proportions before and after the intervention are the same for each race

Data interpretation: If our data feedback / registry intervention is found to produce an effect in less than the 4 Cancer Centers, it will prompt further examination of the factors that moderate or mediate the relationship between the intervention and completion of cancer treatment. Thus, by conducting an embedded randomized cohort-control study of the Cancer Communicator intervention component, we may be better able to provide more information about the dimensions along which these interventions can or cannot be generalized.

hypothesis 2c. a cancer communicator who utilizes active listening and teach-back methods during discussions about lung cancer surgery with newly diagnosed, early stage patients will increase the rate of surgery in African-American patients more than Caucasian patients compared to usual care.

We will compare post intervention, unadjusted, surgical rates between African-American and White lung cancer patients using chi-square analysis as discussed under Aim 1. We will also perform the maximum rate analysis stratified by race. The regression models described above under Aim 1. We will also apply these analyses to patients in the communicator group alone selecting patients on an intention to treat basis.

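### The before rate counts all diagnosed cases but the after rate counts only enrollees, so who enrols can move the before/after change and, because Black patients are oversampled, the racial gap

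*Protocol*

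**What the plan says.** Before period. Protocol section D plans a chart review for 2008 and 2009: "We will review all patients diagnosed with stage I or II, non-small cell cancer to serve as a baseline for surgical rates". "Charts will be selected using appropriate ICD-9 billing codes", and "Data will be collected in an aggregate manner and no linkage files or specific patient identifiers will be maintained". No consent is involved, so in intent this is a census of diagnosed cases.

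After period. Protocol section A limits the registry to enrollees: "All patients with Stage I or II non-small cell lung cancer who enroll in the study will be entered into real time registries". For Aim 2 the SAP (section 6) states "We will both limit analyses to the cancer communicator control group and do an all enrollee analysis". On the size of that group, protocol section E.2 has "estimated an overall recruitment rate of 50%, we will be able to recruit 165 stage I and II patients per year combining all study sites"; section C gives 70% instead.

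Comparisons. Protocol section E: "Lung cancer surgery rates in the control groups will be compared to historical controls at the individual sites". SAP Aim 2 tests the registry and feedback by "contrasting the proportions before and after the interventions" and then adds race and race-by-time terms. The SAP text under hypothesis 1b adds a Pearson chi-square of pre- against post-intervention rates, and Aim 3 adds a before/after analysis with the Aim 1 covariates.

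Race. Section E.2 sets a 30% goal for Black enrolment by oversampling. SAP section 7 uses 159 Black and 337 White patients.

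**The concern.** The two rates have different denominators. Even with identical eligibility criteria, roughly half of the after-period cases would be missing from the after rate, while their counterparts are present in the before rate. The SAP describes no step that counts surgery among non-enrolled cases, compares them with enrollees, or weights for enrolment. Protocol section E defends historical controls by flat national surgery rates. That answers a worry about time trends, not one about who is counted.

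At stake are the control-versus-historical comparison, the pre/post chi-square, hypotheses 2a and 2b, and the before/after part of Aim 3. Aim 2 is the most exposed, because its question is the change in the racial gap and oversampling makes the counted share differ by race.

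**Working it through.** **Inputs.** The 2007 table (protocol C) gives 63 + 141 + 57 + 66 = 327 cases a year. Of these 11 + 24 + 14 + 17 = 66 are African-American and 261 other. Over three years that is 981, 198 and 783.

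**The plan's own figures.** 0.50 × 327 = 163.5 a year and 490.5 in three years, close to the stated 165 and 496. So the accrual target is consistent with 50% of these cases: 496/981 = 50.6%. The power statement also reproduces. For a two-sided one-sample test, Φ[(0.06√496 − 1.96√(0.63 × 0.37)) / √(0.69 × 0.31)] = 80.0%. The plan's target effect is therefore 6 points.

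**Size of the shift.** Let f be the enrolled fraction, E the rate in enrollees and N the rate in non-enrollees. The all-case rate is fE + (1 − f)N. Using E in its place shifts the result by (1 − f)(E − N) = (1 − f)d. At f = 0.506, d = 0.06/0.494 ≈ 12 points reproduces the whole target effect.

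**By race.** The gap shift is (f Black − f other) × d, if d is the same in both races.

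| Enrolled, Black/other | Cases | f Black | f other | Gap shift |
|---|---|---|---|---|
| 159/337 (SAP 7) | 198/783 | 0.80 | 0.43 | 0.37d |
| 149/347 (30% goal) | 198/783 | 0.75 | 0.44 | 0.31d |
| 159/337 | 20% more (assumed) | 0.67 | 0.36 | 0.31d |
| 149/347 | 20% more (assumed) | 0.63 | 0.37 | 0.26d |

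The 20% row is needed because section C says the 2007 counts are tissue-proven only and undercount eligible patients. At d = 10 the gap moves 2.6 to 3.7 points. The gap in the previous study was 0.66 − 0.55 = 11 points. A positive d widens the gap and a negative d narrows it.

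**False-positive rate of the crude chi-square.** Assumptions: f = 0.50, before rate p0 = 0.63 (the previous study's rate, used only as an illustration), after rate p1 = 0.63 + 0.5d, and 500 charts (midpoint of 4 × 100–150). Chance of a significant rise = Φ[(p1 − p0 − 1.96 × SE0)/SE1], with SE0 the pooled and SE1 the unpooled standard error. Here d is the overall enrollee minus non-enrollee difference.

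| d (points) | 496 enrollees | 248 controls (1:1 assumed) |
|---|---|---|
| 0 | 2.5% | 2.5% |
| 5 | 13% | 10% |
| 10 | 38% | 27% |

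For example, at d = 10 with 496 enrollees, p1 = 0.68, SE0 = SE1 = 0.0301, and Φ[(0.05 − 0.0590)/0.0301] = 38%. With 400 to 600 charts that figure runs from 35% to 41%. At f = 0.70 and 496 enrollees the chances are 7% and 17% for d = 5 and 10. A negative d gives false falls of similar frequency. It also hides benefit: at d = −10 a real 6-point rise would appear as 6 − 5 = 1 point.

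**Race mix.** Oversampling also changes the crude overall rate. With rates of 0.55 and 0.66, moving from 66/327 to 159/496 Black patients lowers it from 63.8% to 62.5% with no selection within race. A race term removes this part. It does not remove selection within race.

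**The case against.** Several points on the other side are sound.

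- **Direction.** A reader might infer from protocol section E.2 that hard-to-reach patients resist surgery, are missing from the after rate, and so make d positive. The documents do not support that. The same text describes the CT search, which is designed to find and enrol those patients and put them in the registry.
- **The available rates do not settle the sign.** The 2007 table averages 71% surgery when weighted by site; the previous enrolled study had 63%. This might suggest a negative d. But section C says the earlier study included patients without tissue who refused surgery or dropped out, so the difference mixes eligibility with enrolment.
- **Refusal.** Section C reports 11% refusal with no racial difference. This covers only patients who were approached, not those never found or approached, and it cannot offset unequal fractions created by oversampling.
- **Percentages by race.** The 80% and 43% are not plan figures. They divide planned enrollees, some without tissue, by tissue-proven cases. The ratio of the shift in other patients to that in Black patients is 0.57/0.20 = 2.9 on those inputs, but 0.63/0.37 = 1.7 with the 30% goal and 20% more cases. The imbalance shrinks but stays.
- **Adjustment.** Growth models with race terms (Aim 2) and covariates (Aim 3) are planned, so the error rates above describe the crude test only. However, chart-review patients have no interview measures such as trust or perceived communication, and aggregate collection may limit patient-level adjustment.
- **Scope of 2b.** The real-time registry holds only study patients, so an all-case rate dilutes the effect that 2b tests. This stands, and it limits the fix.

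**Conclusion.** The mismatch of denominators is in the text and holds. It exposes the historical comparisons to selection by enrolment; it does not show a known bias, because d is not given. The shift is (1 − f) × d overall. It is 0.26–0.37 × d in the racial gap if d is equal in both races and true cases are between the 2007 counts and 20% above them. Differences of 5 to 10 points, which are assumed, are enough to raise the crude test's upper-tail error from 2.5% to 13–38% with all enrollees, or 10–27% with controls only.

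A reader might go further and conclude that the before/after tests will show a false improvement, or that the trial's main result is compromised. Neither follows: the sign of d is unknown, and communicator versus usual care is compared within enrollees, so this problem does not touch it. The power calculation uses the previous study's rate rather than the chart review, so it is a separate historical comparison.

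**What to change.** Add to the SAP an all-case before/after contrast of four-month surgery, overall and with a race-by-period term. Use one source and one case definition in both periods: either the ICD-9 aggregate review in both, or the local cancer registries in both, not one for each.

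- **Hypothesis 2a:** make this contrast the main evidence, since the checklist and feedback go to all providers and so can act on all cases.
- **Hypothesis 2b:** make it a required companion to the enrollee analysis, because the registry covers enrollees only.
- **Reporting:** give surgery rates of enrollees beside those of all site cases, by race, and state that enrollee-versus-historical contrasts may reflect who enrolled.

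The cost is SAP wording and a modest aggregate tabulation by race at four sites, of a kind they already supply for the 2007 table. There are two drawbacks. Non-enrolled cases have no interview covariates. The all-case rate also dilutes the registry and communicator effects: at 1:1 allocation (assumed) the communicator would reach about 0.5 × 0.5 = a quarter of cases.
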